We have administered smoked cannabis containing 10mg THC in a prior study (Spindle, 2018) (IRB00035394). In that study, 10mg THC produced discriminative drug effects but did not produce substantial impairment or other negative effects which is why it was selected for this study. This dose also did not produce any adverse events. Following inhalation of smoked cannabis containing 10mg THC, participants self-reported an increase in pleasant drug effects (e.g., mean peak rating of 42.4 for "pleasant drug effect", on 100-point VAS) but subjective ratings of negative effects (e.g., "anxious/nervous", "unpleasant drug effect") remained largely unchanged; 10 mg THC also did not impair cognitive or psychomotor functioning compared with placebo. In another recent study in our laboratory (IRB00101744) that included heavy cannabis users, a smoked 25 mg THC dose produced a moderate drug effect (Mean peak VAS "Drug Effect" rating = 58 of a possible 100) and no adverse events or significant impairment of cognitive function was observed.

Participants will administer nicotine *ad-libitum* in this study using their preferred brand of tobacco cigarettes or the JUUL, the most popular e-cigarette on the market today (King et al., 2018). Tobacco cigarettes and JUUL e-cigarettes will be purchased by study staff from commercial retail tobacco outlets. JUUL pods will be tobacco flavored and will contain nicotine concentrations of either 3% (35mg/mL) or 5% (59mg/mL). Since participants in this study will be regular cigarette smokers and e-cigarette users, and since they will be able to titrate their nicotine dosage during the *ad-libitum* period, we do not anticipate untoward effects from the nicotine doses we will administer. To our knowledge, there is no evidence that the simultaneous administration of nicotine and cannabis will put participants at increased risk of experiencing adverse events.

- b. Justification and safety information if FDA approved drugs will be administered for non-FDA approved indications or if doses or routes of administration or participant populations are changed.
- c. Justification and safety information if non-FDA approved drugs without an IND will be administered.

An IND application has been submitted to the FDA for the administration of cannabis in this protocol (see IRB application).

Study Statistics

Date: July 15, 2022

Principal Investigator: [name]

Application Number: IRB00220975

a. Primary outcome variable.

Primary outcome variable is the amount of nicotine used (determined by total volume of cigarette smoke or JUUL vapor inhaled) after cannabis exposure in each session. We hypothesize that exposure to active cannabis will result in greater nicotine use compared with placebo cannabis.

b. Secondary outcome variables.

Secondary outcome variables include other nicotine use behaviors (amount self-administered and puff topography outcomes), subjective drug effect ratings, cognitive and psychomotor performance, and vital signs (HR, BP). We hypothesize that nicotine use will increase subjective drug effect ratings and decrease cognitive performance after exposure to active cannabis compared with the experimental session in which no nicotine/tobacco products are consumed. We also expect that active cannabis will increase self-reported drug effects compared with placebo cannabis.

c. Statistical plan including sample size justification and interim data analysis.

The proposed sample size of 40 study completers was estimated based on limited prior studies. One study found significant effects of transdermal nicotine and smoked cannabis on subjective drug effects with a sample size of N=20, suggesting that the proposed sample size for this study is adequate to detect interactive effects of nicotine and cannabis on subjective drug effects using a within subjects design (Penetar et al., 2005). Evaluation of pharmacodynamic drug effects using a within-subjects design reduces variability across dose administration sessions and significantly increases statistical power to detect differences on the proposed study outcomes. However, because we have a greater number of dose conditions, and because a primary outcome is amount of drug self-administration rather than self-reported drug effects, we expect the need for a greater sample size in this study.

Initial data analyses will examine whether study completers differ from non-completers with regard to demographic or cannabis use variables. This will inform the generality of the results. We will also examine the data for missing values. When missing data are found in self-report measures we will impute scores by averaging the closest pre and post values when applicable, otherwise missing data will be treated as missing in analyses. Missing data is expected to be rare given that all assessments are conducted via computer and individual items cannot be skipped. However, it is possible that a time point could be missed due to severe drug effects. Data will be evaluated for normal distribution, skewness, kurtosis and appropriate modifications will be made for data that is not normally distributed. All hypothesis tests will be two-sided; α will be set at 0.05. Nicotine/tobacco self-administration data will be analyzed using 2-tailed t-tests comparing the consumption of each nicotine/tobacco product after active versus placebo cannabis pre-treatment. Additional planned comparisons will then be conducted to compare consumption of 3% versus 5% nicotine E-Cig use following active cannabis. Secondary analyses will be conducted using repeated-measures multiple regression to evaluate the effects of nicotine/tobacco product type (None, conventional cigarette, low dose E-Cig, and high dose E-cig) and time as within-subjects factors on subjective drug effect ratings, cardiovascular effects, craving, and cognitive performance effects during sessions in which active (10mg or 25mg THC) cannabis was administered. If sufficient variability in pre-study cannabis use exists in our final study sample, we will conduct exploratory analyses comparing less frequent vs heavy (e.g. daily) cannabis users on primary and secondary outcomes.

d. Early stopping rules.

The study will be stopped if new information is learned that indicates a serious risk to study participants.

7. Risks

a. Medical risks, listing all procedures, their major and minor risks and expected frequency.

A potential risk of smoking cannabis is irritation of the throat/lungs. Acute administration of cannabis can produce tachycardia, intoxication, altered mood, impaired coordination, and cognitive deficits. Given that the dose of cannabis we will administer has demonstrated a favorable safety profile in our prior research, and given that the participants will be experienced with smoking cannabis, the risk of these negative cannabis-related effects or serious adverse events in the laboratory setting is minimal. There is no known risk of overdose or death related to cannabis /THC. In the unlikely event a participant experiences panic and/or paranoid reactions, research staff will engage the person in relaxation exercises and will suspend research procedures until the volunteer has regained comfort. These types of effects are typically of short duration. In the case of an extreme adverse reaction, we will call 911 for emergency treatment. Note that the BPRU is located directly across the street from the Johns Hopkins Bayview ER.

Participants may experience some mild discomfort when not using tobacco/nicotine in the present study. Symptoms of nicotine/tobacco withdrawal are time-limited and typically resolve without clinically significant problems. In case of an adverse event, a study physician is available via pager for assistance. Unpleasant side effects associated with using nicotine/tobacco may include sweating, lightheadedness, dizziness, nausea, and nervousness, though these effects are unlikely to be experienced by participants in the present study because they will be regular users of tobacco products and use will be self-titrated. Given that participants will be regular users of both tobacco cigarettes and e-cigarettes, they will also be familiar with the other more positive acute effects associated with using nicotine/tobacco (e.g., feelings of euphoria, and heightened arousal). We are not aware of any evidence that would suggest simultaneous administration of nicotine and cannabis will put participants at increased risk of experiencing adverse events than use of either drug alone, and, as highlighted in the background, these two substances are widely co-administered in the real-world (Schauer et al., 2015; Schauer et al., 2016).

Exposure to COVID-19 is a risk.

b. Steps taken to minimize the risks.

Participants are not a "vulnerable population" as defined by human subjects protection guidelines; that is, they are not minors, pregnant women, under legal coercion or restriction, or mentally impaired. They are competent adults who provide their voluntary informed consent. Participants will be recruited via media advertisements that clearly state the nature and intent of the study. The consent process will inform the participant in detail of the procedures, time involvement, compensation, risk, and treatment options other than participation in our study. Volunteers will also be instructed that they may withdraw from participation at any time without losing any of the compensation that they have earned to that point.

We feel that the risk of serious adverse events related to cannabis/nicotine exposure in this study is minimal – participants are experienced users of tobacco cigarettes, e-cigarettes, and cannabis, and thus they will be familiar with any acute drug effects they may experience in this study. The doses of THC we are administering (10 mg or 25 mg THC) are on the low end of the ranges used in prior studies and has demonstrated a favorable safety profile (i.e., produced mostly mild subjective drug effects without eliciting adverse effects) among individuals with the cannabis use profile we will recruit in this study. The cannabis doses are expected to produce positive discriminable drug effects without causing impairment of cognitive functioning or adverse events. Given that these individuals regularly use nicotine, they are not expected to experience negative nicotine-related side effects (e.g., nausea). Participants will be able to halt self-administration of either study drug (cannabis or nicotine) if they experience adverse effects. Similarly, study staff may halt the drug administration procedure if untoward drug effects are observed. Such effects

Date: July 15, 2022

Principal Investigator: [name]

Application Number: IRB00220975

are not expected for either nicotine or cannabis at the doses under investigation.

It is unlikely that any adverse event should arise that requires immediate medical treatment. However, in case of an adverse event, participants will be under the supervision of medical/nursing staff throughout the study. The medical and nursing staff at BPRU are trained in CPR and mobile emergency crash carts are available on the same corridor where all experimental procedures will be conducted. The research facility (BPRU) is located directly across the street from the Johns Hopkins Bayview Medical Center Emergency Department, and, in case of an adverse event, we will call 911 for immediate care. The Principal Investigator will be immediately notified of any serious adverse events that arise.

All advertisements and the informed consent process will clearly indicate that this research is designated only for those not seeking treatment, that participation is not a substitute for treatment, and that participation offers no clinical benefit. They will be clearly informed that they will be asked to inhale cannabis and tobacco products (cigarettes and e-cigarettes). Any participant who expresses an interest in receiving immediate treatment for cannabis, tobacco, or other substance use will be referred to a community treatment clinic. If this occurs during the study, their participation in the study will be terminated. As previously described, participants will be instructed that should they withdraw from the study at any point to pursue treatment they will still be compensated for their participation up until that point in the study.

Until risk of exposure to COVID-19 is no longer a public health concern, we will maintain social distancing throughout the study procedures to the extent possible. All staff and study participants will be required to wear PPE appropriate to the nature of the tasks being completed and distance to others (e.g. face masks when maintaining social distancing, face masks, face shields, and disposable gloves when closer than 6ft). We will also minimize the number of staff who come in contact with any single participant to the extent possible based on duties to be performed and staff availability. Our target will be to have each participant only interact with 3 staff (medical staff member for physical evaluation, nurse for blood draws, research staff member for all other procedures).

c. Plan for reporting unanticipated problems or study deviations.

The PI will follow ICH regulations (detailed in *Clinical Safety Data Management, Definitions, and Standards for Expedited Reporting*) regarding reporting of adverse events and all study deviations to the IRB and study sponsor.

d. Legal risks such as the risks that would be associated with breach of confidentiality.

Participants' names will be recorded only on the screening, informed consent, and necessary medical and payment forms. Anonymous participant identification numbers will be used on all other forms and labeling of test results. All information gathered will be kept in locked research staff offices or file cabinets. All medical information obtained will be handled in accordance with HIPAA regulations. Only research staff will have access to participant records. The limits of confidentiality (e.g. suspected child abuse or neglect, or harm to self or others) will be discussed in detail with the participants during the informed consent process. To reduce the likelihood of patient records disclosure, a Certificate of Confidentiality has been obtained for this study.

e. Financial risks to the participants.

This study does not involve patients receiving treatment; therefore, the financial risks are minimal. Participants will be fairly compensated for their time and effort in complying with the study protocol.

Date: July 15, 2022

Principal Investigator: [name]

Application Number: IRB00220975

8. Benefits

- a. Description of the probable benefits for the participant and for society.

The primary benefit of the proposed research is in the knowledge gained regarding the interactive effects of cannabis and nicotine/tobacco. The knowledge can be used to advise the treatment for disordered use of either of these drugs and provide insights into the mechanisms underlying the high rates of co-use of tobacco and cannabis. Because we anticipate relatively minor risks to these cannabis and nicotine-experienced healthy study volunteers, we feel that the proposed research has a positive risk benefit ratio.

9. Payment and Remuneration

- a. Detail compensation for participants including possible total compensation, proposed bonus, and any proposed reductions or penalties for not completing the protocol.

All participants will be compensated \$30 for completing the screening assessment. Participants will be compensated \$200 for completion of each of the seven experimental sessions and will be paid an additional \$300 for completing the study. Total possible earnings for each participant is \$1730. Compensation of this magnitude is appropriate given the nature of this study.

Screening Visit:	\$30
Experimental Sessions	\$200/visit (7 visits = \$1400 total)
Study Completion Bonus	\$300
Total Compensation:	\$1730

Study participants will receive an additional \$200 for any test session that is repeated due to data loss. There will not be any change to the study completion bonus for repeat testing.

10. Costs

- a. Detail costs of study procedure(s) or drug (s) or substance(s) to participants and identify who will pay for them.

The only direct costs to the participants will be their transportation to and from Bayview for each study visit. That cost has been factored into the compensation for participating.

References

- Center for Behavioral Health Statistics and Quality, 2015. Behavioral health trends in the United States: Results from the 2014 National Survey on Drug Use and Health (HHS Publication No. SMA 15-4927, NSDUH Series H-50). Retrieved from <http://www.samhsa.gov/data/sites/default/files/NSDUH-FRR1-2014/NSDUH-FRR1-2014.pdf>.

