Mechanistic hypotheses for the etiology of CT-PSU fall into three general categories (which are not mutually exclusive). The first category posits that CT-PSU results from factors that have been shown to play a role in abuse of a single substance (Vanyukov et al., 2012), including genetics (Stringer et al., 2016), impulsivity (Martinez-Loredo et al., 2015), sensation seeking (Meil et al., 2016), and sociocultural environmental factors (Compton et al., 2014). A related hypothesis is that CT-PSU is facilitated by the shared route of administration of the two substances (Agrawal and Lynskey, 2009), including the user-expressed rationale that tobacco enhances the intensity and duration of cannabis effects and thereby delays the need to re-use (Schauer et al., 2016). A second hypothesis is that nicotine and Δ^9 -tetrahydrocannabinol (THC), the two primary psychoactive constituents of tobacco and cannabis, respectively, produce enhanced reinforcing effects compared to those produced by either substance alone (Panlilio et al., 2013; Tullis et al., 2003). The final set of hypotheses proposes that CT-PSU may result from one substance modulating the aversive effects of the other substance. For example, tobacco co-use may attenuate the initial aversive effects of THC, THC may attenuate nicotine's withdrawal effects (Balerio et al., 2004), or vice versa (Levin et al., 2010). While empirical support for the role of each of these major factors (i.e., shared liability factors, enhancement of reinforcing effects, and amelioration of aversive effects) has been reported (Agrawal et al., 2012; Kohut, 2016; Rabin and George, 2015), clinical research on CT-PSU is still in its infancy, with relatively few controlled investigations offering specific examination of its effects (vs. single drug use). The primary purpose of the present clinical laboratory study is to determine the extent to which acute cannabis intoxication enhances the effects of nicotine-containing products (both e-cigarettes and tobacco cigarettes) and to determine whether the acute effects of cannabis (versus placebo) alters nicotine/tobacco self-administration patterns (e.g., puffing topography). This study will provide key insights into the mechanisms that underlie CT-PSU and ultimately improve treatment for disordered use of both drugs.

Date: July 15, 2022

Principal Investigator: [name]

Application Number: IRB00220975

2. Objectives (include all primary and secondary objectives)

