Objective 1 (Primary): Evaluate whether administration of THC-containing cannabis (versus placebo cannabis) subsequently influences self-administration patterns (time to first self-administration, amount consumed, puffing topography characteristics) of tobacco cigarettes or e-cigarettes.

Objective 2 (Primary): Evaluate whether administration of THC-containing cannabis (versus placebo cannabis) subsequently influences the acute effects (e.g., subjective effects) of tobacco cigarettes or e-cigarettes, nicotine withdrawal symptoms, or craving.

Objective 3 (Secondary): Evaluate whether administration of THC-containing cannabis (versus placebo cannabis) subsequently influences vital signs (e.g., heart rate, blood pressure).

Objective 4 (Secondary): Evaluate whether administration of THC-containing cannabis (versus placebo cannabis) subsequently influences cognitive performance.

3. Background (briefly describe pre-clinical and clinical data, current experience with procedures, drug or device, and any other relevant information to justify the research)

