Nicotine self-administration will occur in an *ad-libitum* fashion for 5 hours following cannabis exposure. During the *ad-libitum* nicotine/tobacco-use period, various puffing behaviors (e.g., puff volume, puff duration, puff number, inter-puff-interval) will be measured using specialized equipment. Acute subjective effects of cannabis/nicotine, cannabis/nicotine withdrawal symptoms, craving, vital signs, and cognitive/psychomotor performance will also be assessed throughout the experimental sessions.

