The Direct Effects of Tobacco Use scale (Spindle et al., 2018) will be used to assess subjective effects specific to tobacco cigarettes or e-cigarettes. Example items from this questionnaire include: "Did the cigarette/e-cigarette make you feel more awake?," "Did the cigarette/e-cigarette help calm you down?," "Did the cigarette/e-cigarette make you dizzy?," "Was the cigarette/e-cigarette pleasant?," "Did the cigarette/e-cigarette reduce hunger?," "Would you like another cigarette/e-cigarette right now?," "Was the cigarette/e-cigarette satisfying?," "Did the cigarette/e-cigarette make you sick?," and "Did the cigarette/e-cigarette taste good?" This questionnaire will be administered before (i.e., baseline), and approximately 5, 30, 60, 90, 120, 180, 240-and 360-min after cannabis exposure.

The Tobacco (Heishman et al., 2003) and Cannabis Craving Questionnaires (Heishman et al., 2001) will assess cravings/withdrawal symptoms for tobacco/nicotine and cannabis, respectively. These questionnaires will be administered before (i.e., baseline), and approximately 5, 30, 60, 90, 120, 180, 240-and 360-min after cannabis exposure.

The Digit Symbol Substitution Task (DSST) will measure psychomotor ability. Participants view a series of nine geometric patterns. Each pattern is numbered (1-9) and consists of three highlighted squares on a 3x3 grid. When the number associated with a particular pattern appears in the center of the screen, participants must replicate the shape of that pattern using an assigned 3x3 section on the keyboard. Task duration is 90 seconds. DSST outcomes include: number of trials attempted, number correct, and percentage of attempted trials completed correctly (Jaeger, 2018). This task will be administered before (i.e., baseline), and approximately 5, 30, 60, 90, 120, 180, 240-and 360-min after cannabis exposure.

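### Objective 2's active-versus-placebo comparison of product ratings has no written analysis, and under free access a raw comparison could not separate a stronger response from more inhaled

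*Combined protocol and SAP*

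**What the plan says.** The Abstract gives two purposes. One is to "determine the extent to which acute cannabis intoxication enhances the effects of nicotine-containing products"; the other is to learn whether cannabis changes how those products are self-administered. Section 2 keeps them apart as two primary objectives. Objective 1 concerns use. Objective 2 asks whether active rather than placebo cannabis "subsequently influences the acute effects (e.g., subjective effects) of tobacco cigarettes or e-cigarettes, nicotine withdrawal symptoms, or craving".

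On measurement, section 4a states: "The Direct Effects of Tobacco Use scale (Spindle et al., 2018) will be used to assess subjective effects specific to tobacco cigarettes or e-cigarettes". That scale and the craving questionnaires are given at baseline and at fixed times from about 5 to 360 minutes after cannabis. Product use is ad libitum, "fashion for 5 hours following cannabis exposure". Section 6a relies on the same freedom in its safety argument: "since they will be able to titrate their nicotine dosage during the" free-access period. Puff volume, number and inter-puff interval are recorded throughout.

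Under Study Statistics, the primary outcome is nicotine use, "determined by total volume of cigarette smoke or JUUL vapor inhaled". The hypothesis is directional: "We hypothesize that exposure to active cannabis will result in greater nicotine use compared with placebo cannabis". The secondary outcomes add: "We also expect that active cannabis will increase self-reported drug effects compared with placebo cannabis". Part c tests consumption of each product, active versus placebo, by t-test. It analyses ratings, craving, vital signs and cognition by repeated-measures regression on product type and time, restricted to sessions with active cannabis.

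**The concern.** There are two linked gaps. First, the ratings model excludes the placebo-cannabis sessions, so a primary objective, and the expectation stated under secondary outcomes, have no matching analysis. Second, whoever writes that analysis will be comparing ratings taken at fixed clock times after unequal and uncontrolled amounts of product. The sponsor expects the amounts to differ in one direction.

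If cannabis leads people to inhale more, ratings such as satisfaction, dizziness or alertness, and craving, may differ between paired sessions even though a given amount of product has the same effect as before. Time to first use is itself an Objective 1 outcome. At an early assessment, one session of a pair may therefore follow product use while the other does not.

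What is at stake is the conclusion. The Abstract treats stronger reinforcing effects as one mechanism of co-use and changed use as a separate question. A raw rating difference cannot tell these apart, and a difference in intake could be reported as enhancement of the product's effect.

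**Working it through.** **1. Match objective to analysis.** Objective 2 needs active-versus-placebo pairs within product. The session list in section 4a supplies three: sessions 2 and 5 (cigarettes), 3 and 6 (3% e-cigarette), and 4 and 7 (5% e-cigarette). Part c of Study Statistics uses these pairs for consumption only. Its ratings model uses sessions 1 to 4, all with active cannabis. No intake term appears there either, so its product-type comparisons also mix product with amount used.

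**2. What 40 pairs can detect.** The plan gives 40 completers and two-sided alpha 0.05, but no effect size, SD, correlation or power, so the sample size cannot be reproduced. For a paired t-test with 39 degrees of freedom, 80% power needs a standardised paired difference of 0.454 (noncentral t). The normal formula gives (1.960 + 0.842)/√40 = 0.443. I use 0.454 as an assumed intake shift d, because it is the shift the primary test would have a fair chance of finding.

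**3. Intake-only model.** Let the paired rating difference equal slope × paired intake difference + noise, with no change in rating per unit inhaled. In SD units the apparent rating effect is r × d, where r is the within-person correlation of the two differences. The noncentrality is r × d × √40. The test is two-sided, so a negative r, as might be expected for craving, gives the same rejection rates.

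| r (assumed) | r × 0.454 | noncentrality | raw contrast significant |
|---|---|---|---|
| 0 | 0 | 0 | 5% |
| 0.3 | 0.136 | 0.86 | 13% |
| 0.5 | 0.227 | 1.44 | 29% |
| 0.7 | 0.318 | 2.01 | 50% |

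At r = 0.3, 0.5 and 0.7, the rates are 9%, 15% and 25% with d = 0.3, and 32%, 69% and 93% with d = 0.8. Simulation agrees with these figures.

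**4. The opposite direction.** Suppose there is a true enhancement of 0.3 SD, but intake falls by 0.454 SD, with r = 0.5. The raw effect is 0.3 − 0.5 × 0.454 = 0.073 SD, significant in about 7% of trials. With no intake shift, 40 pairs would detect 0.3 SD about 46% of the time.

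**5. What adjustment does.** Regress the rating difference on the intake difference and test the intercept. Under the model in step 3, rejections return to about 5%. That result depends on nothing unmeasured driving both intake and rating. In the mirror case the same correlation arises wholly from a shared cause, with d = 0.454 and no enhancement. The raw test then stays at 5%, while the adjusted test rejects in about 12%, 31% and 69% of trials at r = 0.3, 0.5 and 0.7. Its bias is −r × d, that is −0.14, −0.23 and −0.32 SD. In a mixed case (d = 0.8, r = 0.5, loading of 0.5 on a shared cause) the bias is −0.17 SD with 17% rejections.

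**The case against.** The strongest reply is that free access is deliberate. The Background wants to study *chasing* as people do it, and the primary outcome needs self-paced use. Objective 2 asks whether cannabis *influences* product effects; it does not ask about effect per unit inhaled. With randomised session order, the total effect under free access, including any part that runs through intake, is a valid causal contrast. On that reading a rating difference caused by greater intake is not a false positive. This stands, and it is why the raw contrast should be kept and named for what it estimates.

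A reader might infer that the planned analysis will wrongly show enhancement. The documents do not support that. The written ratings model has no placebo-cannabis sessions and cannot produce such a result. The rates in step 3 rest on assumed values of d and r. With little correlation there is almost no inflation, which is plausible for items about taste or pleasantness, and lower intake would hide enhancement.

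The reply also holds against adjustment as a cure. Craving, or wanting another cigarette, both drives puffing and follows from it, and a simple covariate does not resolve that feedback. The mirror case shows the adjusted test can err as badly as the raw one.

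What remains is that the Abstract uses the word *enhances*, that it separates this from changed use, and that Objective 2 has no written analysis.

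**Conclusion.** The concern holds in a limited form. Objective 2's active-versus-placebo contrast on ratings and craving is not specified. If it is run without regard to intake, it estimates the total effect under free access and cannot support a statement that cannabis strengthens the response to a given amount of product. The size is illustrative: 13% to 50% apparent findings instead of 5%, for an assumed intake shift of 0.45 SD, correlations of 0.3 to 0.7, no enhancement and no shared cause. The distortion can run either way.

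It would be too strong to read this as showing that the volume-adjusted result is the true one, or that it should decide the claim. The documents do not say whether intake drives ratings or a common factor drives both. Nor does adjustment supply the missing reference condition: no session pairs placebo cannabis with no nicotine, so cannabis's own effect on general drug ratings and vital signs stays unseparated. This is an inexpensive improvement that changes what the trial may conclude; it is not a flaw in the primary comparison of intake.

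**What to change.** In part c of Study Statistics:

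- Specify the active-versus-placebo contrast on product ratings, withdrawal and craving within each of the three products, using both cannabis conditions.
- State that it estimates the total effect of cannabis under free access. Report it in those words, not as cannabis enhancing the effects of the product.
- Beside it, report a supportive model that adds volume inhaled since the previous assessment as a time-varying within-person covariate. Keep it within product, because a given volume of smoke, 3% vapour and 5% vapour need not carry the same nicotine. Even within a product, volume is only a proxy for dose.
- Attach the caveat that this model conditions on behaviour after cannabis and is biased if something unmeasured, such as momentary craving, drives both puffing and ratings. Say that it does not act as gatekeeper for the Objective 2 conclusion.

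The cost is the contrast that Objective 2 needs in any case, one further model on topography data already being recorded, and some rewording. No new sessions, procedures or participants are needed. The remaining weakness is interpretive: if the two analyses disagree, the trial can describe ratings under free access but cannot settle the mechanism.
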